| 5.5 | Rule of | exclusion criteria of analysis sets | |
| 5.6 | Append | lix A: Vital signs notable criteria | 59 |
| 5.7 | Append | lix B: Clinically notable laboratory values | 60 |
| 5.8 | Append | lix C: Criteria for ECG abnormalities | 60 |
| 5.9 | Append | lix D: Patient-reported Outcome Forms/Instruments | 6 1 |
| | | | 61 |
| | 5.9.2 | Headache Impact Test (HIT-6) scoring | 63 |
| | | | 63 |
| | 594 | Beck Depression Inventory -II (BDI-II) scoring | 65 |

6

| | | | 65 |
|--------|---------|---|----|
| 5.10 | Appendi | x E: Geographic regions | 69 |
| 5.11 | Appendi | x F: MMD derivation, exceptions | 70 |
| | 5.11.1 | Assigning Headache and Migraine Days to Events Spanning Midnight | 70 |
| | 5.11.2 | Spanning Midnight Rules for Multi-Day Events Longer Than Two Days | 70 |
| Refere | ence | | 71 |

List of abbreviations

| AE | Adverse Event |
|--------|--|
| ALT | Alanine Aminotransferase |
| ANC | Absolute Neutrophil Count |
| ANCOVA | Analysis of Covariance |
| AST | Aspartate Aminotransferase |
| ATC | Anatomic Therapeutic Chemical classification |
| BDI | Beck Depression Inventory |
| BOCF | Baseline Observation Carried Forward |
| CMH | Cochran-Mantel-Haenszel |
| C-SSRS | Columbia-Suicide Severity Rating Scale |
| CSR | Clinical Study Report |
| СТС | Common Toxicity Criteria |
| CTCAE | Common Terminology Criteria for Adverse Events |
| DBTP | Double-Blind Treatment Period |
| EA | Everyday Activities |
| ECG | Electrocardiogram |
| eCRF | Electronic Case Report Form |
| eDiary | Electronic Diary |
| EoS | End of Study |
| | |
| FAS | Full Analysis Set |
| GLMM | Generalized Linear Mixed Model |
| HIT-6 | Headache Impact Test |
| IRT | Interactive Response Technology |
| IP | Investigational Product |
| IPW | Inverse Probability Weighting |
| LOCF | Last Observation Carried Forward |
| LPLV | Last Patient Last Visit |
| MAR | Missing at Random |
| MCMC | Markov Chain Monte Carlo |
| MedDRA | Medical Dictionary for Drug Regulatory Affairs |

| MI | Multiple Imputation | | |
|------|--|--|--|
| MIN | Minimum function | | |
| | | | |
| MNAR | Missing Not at Random | | |
| | | | |
| NRI | Non-Responder Imputation | | |
| PD | Protocol Deviations | | |
| | | | |
| | | | |
| PRO | Patient-Reported Outcomes | | |
| PT | Preferred Term | | |
| qm | once a month | | |
| SAE | Serious Adverse Event | | |
| SAF | SAFety analysis set | | |
| SAP | Statistical Analysis Plan | | |
| sc | Subcutaneous | | |
| SD | Standard Deviation | | |
| SOC | System Organ Class | | |
| SSAP | Supplemental Statistical Analysis Plan | | |
| TEAE | Treatment-Emergent Adverse Event | | |
| TFLs | Tables, Figures, Listings | | |
| ULN | Upper Limit of Normal | | |
| UN | Unstructured covariance matrix | | |
| US | United States | | |
| VAS | Visual Analog Scale | | |
| WHO | World Health Organization | | |

1 Introduction

The purpose of this statistical analysis plan (SAP) is to provide details of the statistical analysis according to Section 9 of the study protocol **Protocol v0.0** for AMG 334 Study CAMG334A2302 dated **June 8, 2017** and along with any additional analyses, specifications or deviations from the protocol planned.

The scope of this plan includes the primary, secondary, analyses, which will be executed by Novartis internal statisticians and programmers, if not specified differently. Those analyses will be reported in the CSR.

1.1 Study design

This study uses a single-cohort, 3-treatment arm, randomized (2:3:3 [140 mg: 70 mg: placebo]), double-blind study design in adult patients with episodic migraine.

The following periods are included in the study design:

- Screening period of 2 weeks: to assess initial eligibility,
- Baseline period of 4 weeks: All patients successfully completing the Screening period are invited to participate. Final eligibility prior to randomization and dosing will be assessed based on headache frequency and diary compliance during this period,
- Double-blind treatment period (12 weeks): All patients successfully completing the Baseline period are invited to participate. Eligible patients will be randomized to one of three treatment arms. After randomization/Day 1, visits will occur at four week intervals until Week 12, which is the End of Treatment visit.
- Safety follow-up period: the final visit, a Safety Follow-Up visit, will occur 12 weeks later, at Week 24.

A blinded interim analysis after approximately 50% patients have completed the DBTP (including early withdrawals) will be conducted to re-estimate the sample size by providing information on the variance for this trial relative to the planning assumptions to account for potential higher variability in Asian countries/new sites.

End of Trial (Last Patient Last Visit, LPLV) will occur when all patients have completed their last visit.

Approximatively 880 patients will be randomized (330 in placebo, 330 in AMG334 70mg and 220 in AMG334 140mg), stratified by prior prophylactic migraine medication treatment failure (prior prophylactic migraine treatment failure, due to efficacy or tolerability, vs no prior prophylactic migraine treatment failure).

The primary analysis and all other efficacy and safety analyses will be conducted at the end of study after the database lock; i.e., at the time point when all patients have completed their last visit.

Figure 1-1 Study Design Schematic

| Screen | Baseline | Double-Blind Treatment | Follow-Up |
|---------|----------|------------------------|-----------|
| 2 weeks | 4 weeks | 12 weeks | 12 weeks |

1.2 Study objectives and endpoints

Table 1-1 Objectives and related endpoints

| Objective(s) | Endpoint(s) | |
|---|--|--|
| Primary objective(s) | Endpoint(s) for primary objective(s) | |
| • To evaluate the effect of AMG 334 compared to placebo on the change from baseline in monthly migraine days, in subjects with episodic migraine | • Change from baseline in monthly migraine days at the last month (Month 3) of the double-blind treatment period (DBTP) | |
| Secondary objective(s) | Endpoint(s) for secondary objective(s) | |
| • To evaluate the effect of AMG 334 compared to placebo on the proportion of subjects with at least 50% reduction from baseline in monthly migraine days | • Achievement of at least a 50% reduction from baseline in monthly migraine days at Month 3 | |
| • To evaluate the effect of AMG 334 compared to placebo on the change from baseline in monthly acute migraine-specific medication treatment days | • Change from baseline in monthly acute migraine-specific medication treatment days at Month 3 | |
| • To evaluate the safety and tolerability of AMG 334 | • Adverse events, clinical laboratory values, vital signs, and anti-AMG 334 antibodies | |
| • To evaluate the effect of AMG 334 compared to placebo on change from baseline in headache impact scores as measured by the Headache Impact Test (HIT-6) | • Change from baseline in headache impact scores as measured by the HIT-6 at Month 3 | |

2 Statistical methods

2.1 Data analysis general information

The primary analysis will be conducted on all subject data after LPLV (the last Follow-Up Visit) has occurred. Any data analysis carried out independently by the investigator should be submitted to Novartis before publication or presentation.

To account for potential larger than expected variability during the DBTP of the trial, a blinded interim assessment is planned after about 50% of subjects finish their DBTP or early withdraw. Only the standard deviation of the primary variable, change from baseline in monthly migraine days in month 3, based on pooled (blinded) data from all subjects who had the opportunity to complete the week 12 assessment in the trial, will be estimated. The sample size will be increased appropriately, up to an additional 200 subjects, only if the standard deviation is larger than 5.

Unless otherwise stated, summary tables/listings/figures will be presented for each treatment arm in the respective analysis set.

Categorical data will be presented as frequencies and percentages. For continuous data, the number of non-missing observations, mean, standard deviation (SD), median, minimum and maximum will be presented. Summary tables will also be presented by visit wherever applicable.

In general and unless specified otherwise, all parameters of interest will also be listed by treatment arm and presented by country name/center number/patient id (/ visit wherever applicable).

For efficacy endpoints, graphs will display results where it is appropriate.

General information on treatment arm handling, decimal places and other output-related information will be specified in tables, figures and listing (TFLs) shells accompanying this analysis plan.

Randomization will be stratified by prior prophylactic migraine medication treatment failure (prior prophylactic migraine treatment failure, due to efficacy or tolerability, vs no prior prophylactic migraine treatment failure). Stratification factor used as covariate in the analysis will use the values used for randomization unless otherwise noted.

Statistical analysis of all data will be performed using SAS® statistical software (SAS Institute, Cary, NC, USA.) version 9.3 or higher.

Final and interim analyses described below will be performed by Novartis, unless otherwise noted.

2.1.1 General definitions

Study drug

Novartis will supply the investigational product listed below

- AMG 334 70 mg/1 mL pre-filled syringe
- Matching placebo in 1mL pre-filled syringe, identical in appearance

Two injections of AMG 334 70 mg (equaling 140 mg total dose), one injection of AMG 334 70 mg and one of placebo or two injections of placebo will be administered at each dosing visit. The matching Placebo to AMG 334 pre-filled syringe will have the same appearance as the investigational drug. Each syringe will be packaged individually in double blinded fashion for the double-blind treatment period.

2.1.1.1 Study dates

eDiary Device Assignment Date

The date on which an eDiary device is assigned to a subject for the first time after completion of initial screening at week -4 visit.

Randomization (Enrollment) Date in DBTP

Randomization (Enrollment) Date in DBTP is the date on which a subject is assigned to one of the treatments through IRT in DBTP.

First IP Dose Date

The first IP dose date is the date on which a subject is administered the first dose of IP following randomization, which may be the same day or after the randomization date. For subjects who are randomized but not dosed with double-blind IP after randomization, first IP Dose Date is considered missing.

Last IP Dose Date

The last IP dose date for each subject is defined as the latest date IP is administered.

Subject-level End of Study (EOS) Date

The end of study (EOS) date for each subject is defined as the last date on which the subject participated in the study. The date will be recorded on the Study disposition eCRF page.

Subject-level End of Treatment (EOT) Date

The end of treatment (EOT) date for each subject is defined as the end of the treatment phase. The date will be recorded on the Treatment disposition eCRF page.

2.1.1.3 Arithmetic calculations

Change from Baseline in Monthly Efficacy Measurement

The change from baseline in monthly efficacy measurement is the monthly efficacy measurement in the monthly interval prior to the given time point minus the baseline monthly efficacy measurement. Please, refer to the monthly intervals for efficacy endpoints defined in Table 2-3. For example, change from baseline in monthly migraine days in the last month (month 3) of the double-blind period will be calculated based on the following:

(Monthly migraine days in the last month of the DBTP) – (monthly migraine days during the baseline phase)

If the baseline or post-baseline value is missing, then the change from baseline is set to be missing.

Percent Change from Baseline

The change from baseline divided by baseline and multiplied by 100:

(post-baseline – baseline) * 100 / baseline

Response rate 50% (75% / 100%) will be defined as a decrease from baseline score value of at least 50% (75% / 100%).

Duration of Migraine

The duration of migraine in years (migraine with aura or migraine without aura, whichever is earlier) is calculated by the following formula: current age (in years) - age at migraine onset (in years).

If the current age or the age at migraine onset is missing then duration of migraine will be missing.

Duration of exposure to AMG 334

For all calculations of exposure, dose date refers to receiving dose>0, but can include partial doses.

The duration of exposure is computed as min(last DB dose date+27, EoS Date) – First Dose Date+1.

Compliance with the eDiary

The protocol requirement is 80% compliance in 28 days. That means a minimum 23 diaries must be completed within 28 days. Compliance to eDairy at each month is calculated as

- (Number of eDiary entered in baseline period or between IP doses/28days)*100% if the number of actual days in Baseline period or between IP doses interval is <= 28 days
- (Number of eDiary entered in baseline period or between IP doses/ number of actual days in Baseline period or between IP doses interval)*100% if the number of actual days in Baseline period or between IP doses interval is > 28 days

2.1.1.4 Disease characteristics

Treatment Failure of Prior Migraine Prophylactic Medications

Treatment failure of prior migraine prophylactic medications is determined by "Reason for ending medication" as "Lack of efficacy" (with therapeutic dose) or "Lack of tolerability" in the Prior Migraine Prophylactic Medication eCRF page.

Prior migraine prophylactic medications are classified in 7 categories (as per protocol) and one additional category for other migraine prophylactic medications:

- Category 1: Divalproex sodium, sodium valproate
- Category 2: Topiramate
- Category 3: Beta blockers (for example: atenolol, bisoprolol, metoprolol, nadolol, nebivolol, pindolol, propranolol, timolol)
- Category 4: Tricyclic antidepressants (for example: amitriptyline, nortriptyline,
- protriptyline)
- Category 5: Serotonin-norepinephrine reuptake inhibitors (for example: venlafaxine, desvenlafaxine, duloxetine, milnacipran)
- Category 6: Flunarizine, verapamil
- Category 7: Lisinopril, candesartan
- Category 8: Other migraine prophylactic medication (for example: Botulinum toxin)

For medications entered as free text, categorisation will be provided by clinical team, confirmed by Medical Lead, prior DBL.

The number of failed prior prophylactic treatments is the number of categories with at least one failed prior migraine prophylactic medication.

2.1.2 Visit and analysis windows

Visit window

Since the actual visit for a subject may not exactly coincide with their targeted visit date, the actual visit date is mapped to a study visit.

The next study day window will be utilized to define study visit for lab, vital signs, ECG, C-SSRS and some PROs collected during office visits (HIT-6, BDI-II, BDI-II

| Study visit | Target Day | Study Day | |
|------------------|---|---|--|
| Baseline | See baseline assessr baseline definition) | nent of the Study (Section 2.1.1.2, | |
| Week 4 | 28 | 16-43 | |
| Week 8 | 56 | 44-71 | |
| Week 12 | 84 | 72-99 | |
| Safety follow-up | Safety follow-up sho visit windows descr 'safety follow-up' fo Table 2-2. Target day: last IP d | Safety follow-up should be excluded from the analysis visit windows described above and summarized under 'safety follow-up' for safety analyses only. Refers to Table 2-2. Target day: last IP dose date + 16 weeks | |

 Table 2-1
 Study Visit Windows

For safety endpoints (like lab, vital signs) except ECG, when assessment value for scheduled visit and unscheduled visit are both present within the same analysis window, scheduled visit value should be used. Unscheduled visit will only be used when there is no measurement from the scheduled visit in the defined window. In case of multiple assessment values among the same type of visit (ie, scheduled vs. unscheduled) within the same analysis window, the closest to the scheduled visit day will be used. In case of equal distances (e.g same day), the latest assessment value will be used. The exception is an assessment at early study withdrawal visits along with another assessment within a window. In such cases, the early-withdrawal assessment will be used. For ECG, the same strategy will be applied except that no prioritization of scheduled visit will be made.

In case of multiple assessments on the same day for PROs (including C-SSRS), the first assessment will be used. For C-SSRS, the first complete assessment performed with the electronic version ("Since last visit" recall period) or supplemental data collected on the CRF page will be used. In case of multiple days with assessments within an analysis window (for post-baseline visit) for PROs and C-SSRS, the day the closest to the scheduled visit day will be used.

Study phases

For safety analyses which are summarized by study phase (AE, antibody, laboratory, vital signs, ECG and C-SSRS), or during the entire study (anti-AMG334 antibody), analysis windows will be set up based on study phase:

Table 2-2Study Phases for Safety analysis

| | • | • • | | |
|-------------|---|-----------------|-----------------------|--|
| Study Phase | S | tart Time Point | End Time Point | |
| | | | | |

| Double-blind Treatment Period | For AE, concomitant medications: Study Day 1 Otherwise: Study Day 2 | For AE, concomitant medications: MIN (EoS date, last IP dose date + 27 days) Otherwise: MIN(EoS Date, MAX(last IP dose date + 27 days, EoT date+14 days)) |
|----------------------------------|---|--|
| Safety follow-up | For AE, concomitant medications: last IP dose date + 28 days Otherwise: MAX(last IP dose date + 28 days, EoT date+15 days) | For AE, concomitant medications: MIN(EoS Date, last IP dose date + 16 weeks) Otherwise: MIN(EoS Date, last IP dose date + 16 weeks +14 days) |
| Entire Study | For AE, concomitant medications: Study Day 1 Otherwise: Study Day 2 | For AE, concomitant medications: MIN(EoS Date, last IP dose date + 16 weeks) Otherwise: MIN(EoS Date, last IP dose date + 16 weeks +14 days) |

Note: all anti-AMG 334 antibody data during all periods will be included in immunogenicity analysis.

Monthly Interval for Efficacy Endpoints (from eDiary)

Monthly efficacy measurements will be calculated based on the subject's monthly investigational product (IP) dosing schedule defined below using eDiary data collected from beginning of the baseline phase (week -4 visit) up to EOT visit (week 12 visit).

| Study Phase | Assessment Time point | Interval Based on Dose | Dates |
|-------------------------------------|--------------------------|---|--|
| | | Start date | End date |
| Baseline Period | Baseline | From eDiary device assignment date (or Week -4 visit) | Day prior to study day 1 |
| Double-Blind Treatment Period | Week 4 | Study Day 1 | Week 4 dose date-1 Study day 28 if Week 4 dose is not received (either missed or IP discontinued prior to Week 4) |

Table 2-3Study Intervals for Efficacy Endpoints

| | | Note: if day 1 dose is the last IP dose subject received, the rest of monthly rates during DBTP will be calculated based on consecutive 28-day interval beginning on study day 29 (ie, 29-56 for week 8, 57- 84 for week 12) |
|---------|--|--|
| Week 8 | • Week 4 dose date Study day 29 if Week 4 dose is not received (either missed or IP discontinued prior to Week 4) | • Week 8 dose date-1 Study day 56 if Week 8 dose is not received (either missed or IP discontinued prior to Week 8) |
| Week 12 | • Week 8 dose date Study day 57 if Week 8 dose is not received (either missed or IP discontinued prior to Week 8) | MIN (Study day 84, EoS) if Week 8 dose is not received MIN (Week 8 dose date + 27, EoS) if week 8 dose is received |

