# 3 Investigational plan

### 3.1 Study design

This study uses a single-cohort, 3-treatment arm, randomized (2:3:3 [140 mg: 70 mg: placebo]), double-blind study design in adult patients with episodic migraine. A screening period of 2 weeks will be used to assess initial eligibility, followed by a 4-week baseline period (the maximum duration for the baseline period is 35 days), during which diary compliance and headache frequency will be assessed for a final eligibility assessment prior to randomization and dosing. After randomization/Day 1, visits will occur at four week intervals until Week 12, which is the End of Treatment visit, Last Patient Last Treatment (LPLT). The final visit, Last Patient Last Visit (LPLV), a Safety Follow-Up visit, will occur 12 weeks later, at Week 24.

A blinded interim analysis after approximately 50% patients have completed the DBTP will be conducted to re-estimate the sample size by providing information on the variance for this trial relative to the planning assumptions to account for potential higher variability in Asian countries/new sites.

End of Trial will occur when the last patient completes their last visit (LPLV) of the study.

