#### 5.6.2 Discontinuation of study treatment

Discontinuation of study treatment for a patient occurs when study drug is stopped earlier than the protocol planned duration, and can be initiated by either the patient or the investigator.

The investigator must discontinue study treatment for a given patient if, on balance, he/she believes that continuation would negatively impact the risk/benefit of trial participation.

Study treatment must be discontinued under the following circumstances:

- Patient wish
- Pregnancy (see Section 6.5.5 and Section 7.6)

- Use of prohibited treatment as per recommendations in Section 5.6.2.
- Any situation in which study participation might result in a safety risk to the patient
- Any laboratory abnormalities that in the judgment of the investigator, taking into consideration the subject's overall status, prevents the subject from continuing participation in the study

If discontinuation of study treatment occurs, the patient should NOT be considered withdrawn from the study, and should continue recording in the eDiary as per protocol. The patient should return to the clinic as soon as possible, after discontinuation of study drug, for a study treatment discontinuation visit. Treatment discontinuation visit assessments detailed in the "unplanned treatment discontinuation visit" in Table 6-1 should be completed and recorded in the appropriate CRF. The investigator must determine the primary reason for the patient's premature discontinuation of study treatment and record this information on the appropriate CRF.

After study treatment discontinuation, at a minimum, in abbreviated visits, the following data should to be collected at clinic visits or via telephone visits:

- new / concomitant treatments
- adverse events/Serious Adverse Events

If the patient cannot or is unwilling to attend any visit(s), the site staff should maintain regular telephone contact with the patient, or with a person pre-designated by the patient. This telephone contact should preferably be done according to the study visit schedule.

The investigator must also contact the IRT to register the patient's discontinuation from study treatment.

If study drug discontinuation occurs because treatment code has been broken, please refer to Section 5.5.9. Patients who are prematurely withdrawn from the study will not be replaced by an equal number of newly enrolled patients.

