#### Confidential

#### Novartis Clinical Trial Protocol (Version 00)

#### Page 35 Protocol No. CAMG334A2302

Period	Scree	ning			Treatm	nent		Follow-Up
Visit Name	Screening	Baseline	Treatment	Week 2 	Week 4	Week 8	End of Treatment	Follow-Up
Visit Numbers 	1	20	110	120	130	140	150 and TD/PSD	1999
Days	-42 to -28	-28 to -1	Day 1	14	28	56	84	168
Weeks	-6 to -4	-4 to -1	1	2	4	8	12	24
Healthcare Resource Questionnaire					X 			
Headache Impact Test (HIT-6)			Х		Х	Х	Х	
	_				-			
Adverse Events9			Х	Х	Х	Х	Х	х
Serious Adverse Events 	Х	Х	Х	Х	Х	Х	Х	Х
Concomitant medications	Х	Х	Х	Х	Х	Х	X	Х
Concomitant therapies	Х	Х	Х	Х	Х	Х	Х	Х
Study completion information							Х	Х

 Visit structure given for internal programming purpose only

 Telephone visit.

 Height collected at screen visit only. Weight collected at screen, baseline, and End of Treatment Visit. Blood pressure, pulse and body temperature collected at every visit.

 Hepatitis testing consists of Hepatitis B Core Antibody (HepBcAb), Hepatitis B Surface antigen (HepBsAg), and Hepatitis C virus antibody. If the result for HepBcAb is positive and HepBsAg is negative, additional testing for Hepatitis B virus DNA by Polymerase Chain Reaction (PCR) is necessary. If both are positive, no additional testing is necessary.

 Patients will record headache and headache medication information daily, using the provided eDiary platform.

 To be completed by the patient after each headache.

 Completed daily via the eDiary.

 Adverse Events will be collected from the randomization (Visit 110) through the end of the Follow-Up Period (16 weeks after the last dose of study drug). Events occurring between screen and the first dose of investigational product should be captured as medical history, if warranted.

 SAEs will be collected after signing of the informed consent through the end of the Follow-Up Period (16 weeks after the last dose of study drug).

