2.1.3.2 Safety endpoints

Subject Incidence

The subject incidence for a given event in a given period is defined as the number of subjects with at least one reported occurrence of the event divided by the number of subjects who entered that period. For subjects with multiple occurrences of the same event, the event will only be counted once per subject.

Exposure-Adjusted Subject Incidence Rate

The exposure- adjusted subject incidence rate for a given event in a given period is defined as the number of subjects with at least one reported occurrence of the event in a given time period divided by total subject years at risk in that period. The time at risk for each subject will differ for each adverse event. For subjects with events, only the time until the first event contributes to the total subject years at risk. For subjects who do not experience the event, the time at risk will be calculated based on the safety analysis study window (Table 2-2). This rate will be presented per 100 subject years. For subjects with multiple occurrences of the same event, the event will be only counted once per subject.

Treatment-Emergent Adverse Event (TEAE)

Adverse Events (AEs) recorded on the Adverse Events eCRF page that occurs on or after first dose of investigational product and up to and including 112 days after the end of IP (16 weeks after the last dose of IP).

Serious Adverse Event (SAE)

SAEs determined by the flag indicating if the adverse event is serious on the Adverse Events eCRF page will include those that occur after signing of the informed consent and up to and including end of study.

Treatment-Emergent Serious Adverse Event

A treatment-emergent serious adverse event is an SAE considered to be treatment-emergent.

Treatment-Related Adverse Event

A treatment-related AE is defined as a treatment-emergent adverse event that is considered by investigators to have reasonable possibility that it may have been caused by IP as determined by the flag indicating that there is a reasonable possibility that the AE is related to investigational product on the Adverse Events eCRF page.

Treatment-Related Serious Adverse Event

A treatment-related serious adverse event is an SAE considered to be treatment-related.

Columbia-Suicide Severity Rating Scale (C-SSRS)

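### SAP Table 2-2 can close the follow-up and entire-study phases before the final visit for patients who stop dosing early but stay in the study

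*SAP*

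**What the plan says.** The documents give two anchors for the end of follow-up.

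**Fixed anchor.** Protocol 3.1 states that "a Safety Follow-Up visit, will occur 12 weeks later, at Week 24", and protocol Table 6-1 puts that visit at Day 168. SAP 1.1 repeats Week 24, and SAP 2.3.1 defines study completion by the Week 24 visit.

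**Last-dose anchor.** Footnotes 9 and 10 of protocol Table 6-1 collect AEs and SAEs "through the end of the Follow-Up Period (16 weeks after the last dose of study drug"). SAP Table 2-1 gives the safety follow-up visit this timing: "Target day: last IP dose date + 16 weeks".

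**Analysis phases.** SAP Table 2-2 follows the last-dose anchor. For AEs and concomitant medications, both the follow-up and the entire-study phase end at "MIN(EoS Date, last IP dose date + 16 weeks"). For other safety data they end at "MIN(EoS Date, last IP dose date + 16 weeks +14 days"). A note under the table exempts antibody data.

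**Patients who stop drug.** Protocol 5.6.2 says that "the patient should NOT be considered withdrawn from the study, and should continue recording in the eDiary as per protocol".

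**SAEs.** SAP 2.1.3.2 includes SAEs occurring "after signing of the informed consent and up to and including end of study". Protocol 7.2.2 requires SAEs to be reported until the last study visit. SAP 2.7.1 summarises SAEs and deaths by phase.

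**The concern.** For a patient who takes all three doses on schedule, the two anchors give the same day and nothing is lost. For a patient who stops after one or two doses and stays in the study, they separate. Neither document says which one sets that patient's final visit.

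If the visit takes place at Week 24, the phase called entire study has already closed, and data from a scheduled visit reach no phase summary. For SAEs and deaths, the phase limit also contradicts the SAP's own definition of what is included.

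The patients concerned stopped dosing early, and protocol 5.6.2 lists safety risk and laboratory abnormalities among the reasons for stopping. Their late data should be in the follow-up and entire-study tables.

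**Working it through.** **Inputs.** Doses are given at Day 1, Week 4 and Week 8, each within 5 days of schedule (protocol 5.5.4). Week 4 is taken as Day 28 (Table 6-1) or Day 29 (counting 28 days from Day 1), and Week 8 as Day 56 or 57. The final visit is Day 168. The EoS date is assumed not to be limiting, meaning that the patient attends at Day 168.

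**Formulas.** AE phase end = last dose + 112. Other safety data phase end = last dose + 126.

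**Where the anchors agree.** Week 8 plus 16 weeks is Week 24: 56 + 112 = 168, or 57 + 112 = 169 on the other day count.

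**Where they part.**

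| Last dose | AE phase ends | Short of Day 168 by | Other data phase ends | Day 168 inside? |
|---|---|---|---|---|
| Day 1 | 113 | 55 days | 127 | No, 41 days late |
| Week 4 (Day 28/29) | 140/141 | 27–28 days | 154/155 | No, 13–14 days late |
| Week 8 (Day 56/57) | 168/169 | 0 | 182/183 | Yes |

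Across the dosing tolerance, a Week 4 last dose falls between Day 23 and Day 34. The window for other data then ends between Day 149 and Day 160, still 8 to 19 days before the visit. In general, Day 168 is inside that window only if the last dose was on Day 168 − 126 = Day 42 or later.

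A full-course patient dosed 5 days early at Week 8 (Day 51/52) has an AE phase ending on Day 163/164, 4–5 days before Day 168.

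**Can another phase pick up the data?** The double-blind phase for other data ends at "MIN(EoS Date, MAX(last IP dose date + 27 days, EoT date+14 days")). With end of treatment at Day 84 that is Day 98. To reach Day 168 it would need an end-of-treatment date of Day 168 − 14 = Day 154. The entire-study phase has the same end point as safety follow-up. In SAP Table 2-1 the last numbered window, Week 12, closes at Day 99, and the follow-up row refers back to Table 2-2. So no phase takes these data.

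**If the visit instead follows the last dose.** At last dose + 112 it falls on Day 113 or Day 140/141, inside windows that end on Day 127 or Day 154/155. The visit data are then captured, but the timing departs from protocol 3.1 and Table 6-1 and from SAP 1.1 and 2.3.1.

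**Check of the fix.** With the phase ending at the EoS date, the final visit falls inside safety follow-up after one, two or three doses, under either timing.

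**The case against.** The best defence is that the last-dose anchor is deliberate and coherent. SAP Tables 2-1 and 2-2 agree with each other and with protocol footnotes 9 and 10, and a fixed time off drug makes follow-up comparable across patients. This stands in part. For non-serious AEs, the 112-day limit matches both the collection rule in footnote 9 and the treatment-emergent definition, and it should stay. It does not reconcile the Week 24 statements, nor the SAE definition that runs to end of study.

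Several stronger readings are tempting, and the documents do not support them:

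- *All early stoppers lose their Week 24 data.* Patients who leave the study have the final assessments as soon as possible (protocol 6), so they have no Week 24 visit to lose. A patient who misses Week 4 but is dosed at Week 8 has had two doses and is covered.
- *Laboratory and vital-sign data are certain to be collected and then dropped.* After treatment stops, protocol 5.6.2 sets a minimum of concomitant treatments and AEs/SAEs, by clinic or telephone. Day 168 laboratory and vital-sign data may exist but are not guaranteed.
- *The data vanish from the report.* AEs, SAEs and deaths are listed (SAP 2.7.1, 2.7.2). Notable laboratory values and vital signs are flagged and listed (2.7.3, 2.7.4.2). Antibody data are exempt, and no ECG is scheduled at Week 24.
- *Some 44 to 88 patients are affected.* These are 5% and 10% of 880, from the roughly 95% three-month retention in protocol 3.6 and the planned 10% drop-out. Neither is a rate of stopping drug while remaining in follow-up.
- *The safety tables are biased.* Early stoppers keep their earlier data and up to 16 weeks of off-drug AEs in the tables, and the same rule applies in every arm. Bias towards patients who tolerated treatment is plausible but not shown.

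**Conclusion.** The point holds as an unreconciled pair of anchors, with a definite consequence when Table 2-2 is followed literally. For a patient whose last dose was Day 1 or Week 4, who stays in the study and attends at Day 168, any laboratory, vital-sign and C-SSRS data from that visit enter no phase summary. The shortfall is 41 days after one dose and about 13–14 days after two.

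SAEs and deaths occurring after last dose + 112 days but before end of study are left out of every phase table. This contradicts SAP 2.1.3.2 whenever the EoS date falls after that limit, whichever anchor is meant to set the visit.

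The number of patients cannot be derived from the documents and is probably small. The primary endpoint, type I error and power are untouched. The change is worth making because a phase named entire study should not close before the study's last visit, and the correction is cheap.

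**What to change.** In SAP Table 2-2, end the safety follow-up and entire-study phases at the EoS date for SAEs, deaths, laboratory, vital-sign and C-SSRS data. Keep the 112-day limit as the treatment-emergent flag for AEs. Late SAEs would then appear in the SAE tables without that flag, and a footnote should say so.

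Separately, reconcile protocol 3.1 and Table 6-1, SAP 1.1 and SAP 2.3.1 with footnotes 9 and 10 and SAP Table 2-1, so that the documents state one timing for the final visit of patients who stop dosing early. Protocol 7.2.2 and footnote 10 should be aligned on how long SAEs are collected in these patients. Which timing applies is for the sponsor to decide.

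The cost is a wording change and one derivation, with no new data. Exposure-adjusted rates are unaffected, because SAP 2.7.1 plans them only for the double-blind phase. The small downside is that follow-up values for early stoppers may come about 20 to 24 weeks after the last dose and not 16: (168 − 29)/7 = 19.9 and (168 − 1)/7 = 23.9. A footnote or a column giving time since last dose would make that visible.
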